## **Samples for Performing the Immunological Studies and RCR Testing**

---

All assays to be performed by CICSL and Clinical Pathology are detailed in Section 12.2.

### **8.1.15 Immunological Studies- Correlative Studies**

---

Notify the CICSL prior to sample collection. Notification should be at least 24 hours in advance (the earlier the better) in the form of Outlook calendar notifications by e-mail to [[contact]](mailto:[contact]). CICSL would prefer samples to be delivered before 4 pm each day.

To assess for possible development of T cell responses to the adenovirally transduced NSCs and to evaluate for systemic presence of the NSCs and/or hCE1m6, approximately **30 ml** of blood will be collected in lavender top tubes (liquid potassium EDTA). The samples will be placed on wet ice and delivered to City of Hope's CICSL for processing.

To assess for possible antibody responses to the NSCs and/or adenoviral proteins, approximately **10 ml** of blood will be collected in red top tubes (free of any anti-coagulant reagent). Samples should be kept in an upright position at room temperature for 1 – 2 hours before processing to allow blood to clot. If processing cannot be done the same day, samples should be kept in an upright position at 4°C and processed within 24 hours. Centrifuge the sample at 1000 x g for 15 minutes at 4°C. Remove the serum without disrupting the blood at the bottom of the tube. Serum samples will be aliquoted and distributed to CICSL and Clinical Pathology.

### **8.1.16 Immunological Studies – Suspected NSC Immune Response**

---

If a patient develops an adverse event that is suspected of being due to an immune response to the NSCs, **3-5 ml** of blood will be collected in a red top tube (free of any anti-coagulant reagent) at least twice (separated by approximately 2 days) during the event for analysis of serum cytokine levels via Luminex cytokine panels. Samples should be kept in an upright position at room temperature for 1 – 2 hours to allow blood to clot. Take samples to CICSL for processing. If unable to take to CICSL the same day, samples should be kept in an upright position at 4°C until delivery the next day. For the first sample, communicate to CICSL that the pre-treatment sample is also to be assayed to provide a baseline for comparison.

### **8.1.17 RCR Testing**

---

For RCR testing, at least **10 ml** of blood will be collected from each patient in EDTA treated (lavender top) tubes maintained at room temperature with occasional gentle agitation and sent to City of Hope's CICSL.

## 9 AGENT INFORMATION AND RISKS

---

### **hCE1m6 - NSCs (IND # 16265)**

---

#### **9.1.1 Animal Toxicity Data**

---

All toxicity studies to date in mice have shown no evidence of organ damage or tumorigenicity due to NSCs. Please see sections 2.4.2 and 2.4.3.

#### **9.1.2 Human Toxicity Data**

---

See sections 2.5 and 7.1.2.

#### **9.1.1 Handling**

---

Following thawing and resuspension in the [name] Laboratory, cells are to be maintained at room temperature until administration. Sterile technique is to be used in the handling of cells.

#### **9.1.2 Administration**

---

Intracranial administration---either through direct injection into tumor at the time of surgery, or via a Rickham that is placed in tumor tissue.

#### **9.1.3 Supplier**

---

City of Hope –[name] Laboratory will provide NSCs, already thawed and resuspended (per SOP) for administration. To order cells, call COH extension [name] or email [name] at [[contact]](mailto:[contact]) or her designee.

### **Irinotecan**

---

Irinotecan (CAMPOSTAR) is an FDA approved chemotherapy agent. Please refer to the Package Insert for additional details not provided in this section.

#### **9.1.4 Description**

---

Irinotecan hydrochloride trihydrate {CPT-11, (4S)-4, 11-diethyl-4-hydroxy-9-((4-piperidinopiperidino) carboxyloxy)-1H-pyroano{3',4':6,7}indolzino{1,2-b}quino line-3, 14(4H,12H)dione hydrochloride trihydrate} is a topoisomerase I inhibitor.

#### **9.1.5 Human Toxicity**

---

See section 7.1.4.

#### **9.1.6 Formulation**

---

Irinotecan is supplied in three forms: 2 mL vials containing 40 mg of drug, 5mL vials containing 100 mg of drug, and 15 mL vials containing 300 mg of drug. The drug is supplied in brown vials and appears as a pale-yellow-to-yellow crystalline powder and pale yellow transparent solution when reconstituted.

#### **9.1.7 Storage and Stability**

---

Irinotecan vials must be stored in a cool, dry place, protected from light in a locked cabinet accessible only to authorized individuals. It is stable to the expiration date on its label. Irinotecan is stable for at least 24 hours in glass bottles or plastic bags after reconstitution with D5W.

#### 9.1.8 Handling

Qualified personnel, familiar with procedures that minimize undue exposure to themselves and the environment, should undertake the preparation, handling, and safe disposal of the chemotherapeutic agent.

#### 9.1.9 Administration

Irinotecan will be diluted with D5W to a total volume of 500 ml and infused intravenously over 90 minutes. Nothing else should be added to the bag.

#### 9.1.10 Supplier

City of Hope will purchase irinotecan formulated for human use from a commercial source, but separate supplies for this investigational protocol will be accounted for by the Investigational Drug Service.

## 10 STUDY CALENDAR

---

Table 10, Study Activity Calendar, describes required procedures and provides references where additional information is necessary. All procedures may increase in frequency if clinically indicated or oriented following a toxicity/adverse event. See Section 7.3 for adjustments to the study calendar following a delay of study agent administration.

Study tests and procedures may be done +/- 3 days for patient convenience and scheduling. A window period of +/- 1 day is allowed for intracranial administration of NSCs, but there must still be at least an interval of 2 days between administration of the NSCs and irinotecan.

During the treatment cycle, **on days of agent administration, all safety assessments must be performed and reviewed prior to administration of any study agent.**

**Table 10 Study Activity Calendar**

	Screening b	Cycle 1 a										Cycle 2+					End of Tx g	30-Day Post Tx h	Long Term Follow-Up, Autopsy i
		Day 1	Day 2	Day 3	Day 4	Day 5	Day 8	Day 10	Day 15	Day 17	Day 22	Day 1c,d	Day 3	Day 15 e	Day 17	Day 28 f			
Informed consent j	X																		
Background/medical history k	X																		
Inclusion/Exclusion criteria l	X																		
Histology confirmation	X m	X n																	
Vitals, KPS, neuro & physical exams o	X		X	X							X p			X		X	X	X q	
Adverse event assessment r	X		X	X			X			X p		X	X		X		X	X	
Concomitant meds review s	X		X	X					X p			X		X			X	X	
HLA antibody screening u	X																		
UGT1A1 polymorphism v	X																		
Immunological studies w	X x								X p			X y		X			X		
RCR testing z	X x																		
Coagulation: PT/INR, PTT	X																		
CBC with ANC aa	X			X			X		X p			X c		X c			X		
Comprehensive Metabolic Panel bb	X			X				X p			X c						X		
Serum Pregnancy Test cc	X																		
Chest X-ray and EKG	X																		
Imaging – MRI	X dd	X ee	X ff													X ff	X hh		
Imaging – PET/CT scan of the brain		X gg														X gg	X hh		
Response Assessment ii																X	X ii		
Neurosurgery		X jj			X kk														
Administration of hCE1m6 - NSCs		X ll							X m			X m		X m					
Non-contrast Brain CT		X																	
Dialysate, blood pK collection oo			X	X	X														
IV administration of irinotecan pp			X rr						X			X ss	X tt	X ss	X tt				
Post-Study Tx Medical History uu																		X	
Tissue from autopsy vv																			X

- a. For patients on dose level 1 /-1, Cycle 1 will be a minimum of 30 days to ensure that 14 days have passed between irinotecan doses.
- b. To be performed within 14 days from planned date of surgery, except for MRI (footnote ee) to be performed within 28 days of registration.
- c. Laboratory evaluations to be performed and results reviewed within 2 days prior to agent administration. Laboratory evaluations may be performed at a clinic local to the participant.
- d. 'Start of Cycle' criteria are found in Section 7.2.2. All assessments to occur prior to administration of NSCs (or irinotecan for dose levels 1/-1).
- e. All assessments to occur prior to administration of NSCs (or irinotecan for dose levels 1/-1).
- f. Imaging (brain MRI and PET/CT scans) should at least be done at the end of every 2 cycles (Day 28 -3days).Imaging can be done more frequently than after every 2 cycles to closely follow up on changes of unknown significance seen on a prior brain MRI or PET/CT scan.
- g. End of treatment assessments to be performed within 7 days after last study agent administration or within 7 days after decision to end treatment. Assessments may continue for ongoing reportable adverse events or events resulting in a dose modification.
- h. A contact/visit for review of adverse events, KPS, concomitant medication review, and vital status is to be performed at 30 days +/- 2 days after the last study agent is given. This may be performed via documented phone conversation with a study nurse or clinician. All participants will be followed until resolution or stabilization of any serious or reportable adverse events occurring during treatment or starting within 30 days of last study agent.
- i. Long-term follow-up to occur until death for updated medical history, RCR testing, and tissue at autopsy. Required elements occur at 3 months (+/-14 days), 6 months (+/-14 days) and annually from start of study treatment, and upon patient death. See footnotes z, rr, and ss for details.
- j. Performed by MD attending only. Informed consent process to be fully documented.
- k. Background/medical history – to include review of treatment history for glioma, any ongoing medical conditions and medical history pertaining to eligibility on study and involvement during study.
- l. Inclusion/exclusion criteria. Source documentation providing investigator's confirmation that patient has met all eligibility criteria must be available prior to registration. In addition, source documentation by neurosurgeon that (a) a physical connection between the post-resection tumor cavity and cerebral ventricles is not anticipated, (b) a gross total resection is not anticipated, (c) the prospective participant is able to undergo neurosurgery, and (d) documentation that patient "needs a biopsy/craniotomy" is needed.
- m. Histology confirmation for to be performed by COH pathologist.
- n. Real-time histology confirmation to occur during surgery on fresh frozen section. See section 8.1 for pathology criteria. If confirmation of high grade glioma not obtained, all further study procedures will cease.
- o. Vital signs: Weight, heart rate, blood pressure, respiration rate, temp. Height required only at baseline. KPS not required at Day 2 and 3. See Appendix A for KPS scale.
- p. Participants no longer receiving NSCs (e.g. Dose Levels 1 and -1) may have their Day 15 assessments performed on Day 17, prior to irinotecan dosing.

- q. KPS and vital status only. Vital signs and Neuro-Physical exam are not required.
- r. Adverse events experienced by participants will be collected and recorded from signing of informed consent document up to 30 days of the last dose of study medication. The period for collection and recording of AEs is extended for participants with ongoing “reportable” adverse events that are related to study agent. Adverse event reporting begins for events that occur on Day 1 (day of neurosurgery).
- s. The only concomitant medication that needs to be documented in the case report form is whether the patient is taking dexamethasone (or another corticosteroid), and if so, what the dose is.
- t. For HLA testing, collect blood in 1 red top tube. Maintain at room temperature. Bring samples to COH Histocompatibility Laboratory.
- u. Participants who have already undergone UGT1A1 genotyping may use those results and do not the procedure repeated.
- v. For immunological correlative studies: notify CICSL by e-mail to [[contact]](mailto:[contact]) at least 24 hours in advance of sampling. Collect six 6-ml lavender top (K-EDTA) tubes, keep on wet ice, and send to COH CICSL; collect approximately 10 ml of blood in red top tubes, keep upright at room temperature and process as per Section 8.6.1 before sending to the COH CICSL and Clinical Pathology. On days where study agent is administered, samples are always to be taken prior to agent administration.
- w. If participant is removed (or withdraws) from the trial prior to receiving study agent, the samples are to be discarded.
- x. Cycle 2 only.
- y. For RCR testing, collect two 6-ml lavender top (K-EDTA) tubes (or a volume of 10ml) maintained at room temperature with gentle agitation ~hourly and send to CICSL. On days where study agent is administered, samples are always to be taken prior to agent administration. Notify CICSL by e-mail to [[contact]](mailto:[contact]) in advance of sampling.
- z. RCR testing is required for all patients at 3 months\* and 6 months\* and annually\* thereafter post start of study treatment, whether patient is on treatment or in long term follow-up. For patients still on treatment, assuming there are no delays in treatment, this means RCR testing is to be performed at C4D1 and C7D1. Take RCR testing at most appropriate clinic visit for patients still on study treatment. For patients in long term follow-up, samples may be obtained via local physician and shipped to COH for testing. (\*+/-14 days)
- aa. CBC with ANC: hemoglobin, hematocrit, platelets, total WBC and neutrophils
- bb. Comprehensive metabolic panel: Sodium, potassium, chloride, carbon dioxide, creatinine, urea nitrogen, calcium, glucose, albumin, total bilirubin, alkaline phosphatase, total protein, ALG/SGPT and AST/SGOT.
- cc. Serum pregnancy test only for women of child bearing potential.
- dd. A contrast, non-contrast MRI is to be performed for screening within 28 days from registration. (Day 2 post-surgical MRI will serve as the baseline MRI).
- ee. A pre-surgical planning post-registration MRI **may** be performed if indicated by the neuro-surgeon.
- ff. A contrast, non-contrast MRI will be performed for all patients at least every two months.
- gg. A PET/CT scan will be performed within 7 days after surgery to serve as the baseline scan, and then a PET/CT scan will be performed whenever possible at the time follow up brain MRIs are done.

- hh. Imaging to be performed if the prior assessments occurred > 21 days before decision to end treatment, if patient is agreeable to have this procedure. The absence of this MRI and/or PET/CT scan with corresponding response assessment will not be considered a protocol deviation.
- ii. Response assessment using RANO criteria, at time of imaging and as indicated clinically. Dexamethasone dose to be integrated into response determination. See Section 13 for RANO criteria.
- jj. Neurosurgery will include real-time pathology review and may include Rickham Catheter and/or Microdialysis Catheter placement and/or NSC administration. See section 8.2 for details.
- kk. For participants undergoing microdialysis (procedures A, C, E, G, I, K) only, microdialysis catheter is to be removed following completion of microdialysis by the neurosurgical team. See section 8.3.6 for all relevant information.
- ll. On day of surgery, NSC administration will occur either fully during surgical procedure (craniotomy procedure A-J, biopsy procedure A-F), or will occur both during the surgical procedure **and** following the surgical procedure via the Rickham (biopsy procedures G-J only). Half of the participants in the expansion cohort will not receive Day 1 NSCs (procedure K).
- mm. Dose level 2, 3, 4 (procedures E-J) participants only. Via Rickham catheter. See Section 8.5 for procedure.
- nn. For participants undergoing Microdialysis only (procedures A, C, E, G, I, K). Post surgical non-contrast CT used to confirm appropriate placement of catheter. See section 8.3.1 for details.
- oo. For participants undergoing Microdialysis only (procedures A, C, E, G, I, K). Sampling of blood and dialysate to begin prior Day 3 irinotecan administration and up to 48 hours after irinotecan administration. For the blood pKs, a venous catheter is required. See Section 8.3.2 to 8.3.5 for details.
- pp. Irinotecan administration is detailed in Section 8.4, including required prophylaxis, observation periods and documentation for required elements
- qq. (This has been deleted)
- rr. In order to receive Day 3 irinotecan, participant must have recovered well, per the neurosurgeon (documented in clinical record), from any immediate post-operative effects, and the patient must require  $\leq$  16mg/day of dexamethasone. Otherwise the participant will be removed from all study treatments.
- ss. Dose level 1 and -1 (procedures A-D) participants will have irinotecan administration on Day 1 and Day 15. NOTE: it is imperative that Cycle 1 is extended as needed (e.g. from 28 days to 30 days) to ensure that the Day 1 irinotecan dose occurs 14 days after the previous irinotecan dose.
- tt. Dose level 2, 3 and 4 (procedures E-J) participants only
- uu. Post-Study Treatment Medical History will consist of annual requests from the patient/patient's primary oncologist for clinical information regarding other anti-cancer therapy, progression of disease, survival, as well as information pertaining to de novo cancer, neurologic, autoimmune and hematologic disorders. In addition, unexpected medical problems including information on hospitalizations and medications will be collected. To occur annually (+/-14 days) from the start of study treatment. Alternatively, participants may come into the clinic to provide the previous year's medical history.
- vv. Efforts will be made to obtain tissue at the time of autopsy.

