#### Non-hematological, non-nervous system toxicities

8. Grade 3 toxicity despite maximal medical therapy lasting > 7 days.

9. Grade 3 toxicity resulting in study agent discontinuation (permanently removed from study treatment).
10. Grade 4 toxicity, except grade 4 diarrhea that responds to maximal medical therapy within 3 days.

Please note: An allergic reaction to the NSCs is excluded from the DLT definition, because NSC dose reduction is not appropriate in this situation. The possible occurrence of allergic reactions to the NSCs is addressed by the study stopping rules (Section 5.6).

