#### **6.1.8 REQUIRED Serum electrolyte abnormalities $\geq$ CTCAEv3 grade 3**

If serum chemistries  $\geq$  CTCAEv4 grade 3 or greater:

Patient's potassium, calcium, phosphorous or magnesium should be immediately supplemented or otherwise corrected following the availability of those laboratory results, in order to minimize the time patients have abnormal values.

More frequent testing should be done if clinically indicated, e.g. patient has had prior low values, patient is experiencing gastro-intestinal toxicities or is taking medications that can result in lowering of their potassium, magnesium, phosphorus or calcium levels.

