Thrombocytopenia Grade 2 ( $50 - < 75 \times 10^9/L$ )		Maintain treatment
Thrombocytopenia Grade 3 ( $25 - < 50 \times 10^9/L$ )		Hold treatment until recovery to $\leq$ grade 2 (plts $\geq 50 \times 10^9/L$ ).
Thrombocytopenia Grade 4 ( $< 25 \times 10^9/L$ )		Hold treatment until recovery to $\leq$ grade 1 (plts $\geq 75 \times 10^9/L$ ). Resume treatment with an irinotecan dose reduction of 30 mg/m  .
Neutropenia (ANC) Grade 1 ( $1.5 \times 10^9/L < LLN$ )	Irinotecan	Maintain treatment
Neutropenia (ANC) Grade 2 ( $1.0 - < 1.5 \times 10^9/L$ )		Maintain treatment
Neutropenia (ANC) Grade 3 ( $0.5 - < 1.0 \times 10^9/L < LLN$ )		Hold treatment until recovery to $\leq$ grade 2 (ANC $\geq 1.0 \times 10^9/L$ ). First occurrence: Resume treatment with no dose modifications. Each occurrence thereafter: Resume treatment with an irinotecan dose reduction of 30 mg/m  .
Neutropenia (ANC) Grade 4 ( $< 0.5 \times 10^9/L < LLN$ )		Hold treatment until recovery to $\leq$ grade 2 (ANC $\geq 1.0 \times 10^9/L$ ). Resume treatment with an irinotecan dose reduction of 30 mg/m  .
Febrile neutropenia $\geq$ Grade 3 (ANC $< 1.0 \times 10^9/L$ , fever $> 38.5^\circ C$ )	Irinotecan	Hold treatment until recovery to $\leq$ grade 1 (ANC $\geq 1.5 \times 10^9/L$ ). Resume treatment with an irinotecan dose reduction of 30 mg/m  .
Serum Electrolytes		
Serum Electrolytes $\geq$ Grade 3 Calcium, Potassium, Magnesium, Phosphorous	Irinotecan (via diarrhea)	Provide supportive care per Section 6.7. Maintain treatment per investigator discretion.
Gastrointestinal		
Diarrhea Grade 1 (2-3 stools/day $>$ pretreatment)	Irinotecan	Maintain treatment
Diarrhea Grade 2 (4-6 stools/day $>$ pretreatment)		Hold both study drugs until resolved to $\leq$ grade 1, then resume treatment at pre-hold dose

Diarrhea Grade 3 (7-9 stools/day > pretreatment)	Irinotecan	Event present while on optimal anti-diarrheal therapy: Hold study treatment until the diarrhea decreases to $\leq$ grade 1, and then restart treatment with the dose of irinotecan reduced by 30 mg/m 
Diarrhea Grade 4 ( $\geq$ 10 stools/day > pretreatment)		Event present while on optimal anti-diarrheal therapy: Hold study treatment until the diarrhea decreases to $\leq$ grade 1, and then restart treatment with the dose of irinotecan reduced by 60 mg/m  .
Vomiting or Nausea Grade 1		Maintain treatment
Vomiting or Nausea Grade 2		Maintain treatment

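### Magnesium and phosphorus are named for action at grade 3 or higher, but no scheduled test measures them, so abnormalities are found only by clinically indicated testing

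*Combined protocol and SAP*

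**What the plan says.** Section 6.1.8, which is headed as required, covers serum chemistries at grade 3 or higher. It states that the patient's "potassium, calcium, phosphorous or magnesium should be immediately supplemented or otherwise corrected following the availability of those laboratory results". It then adds: "More frequent testing should be done if clinically indicated, e.g. patient has had prior low values, patient is experiencing gastro-intestinal toxicities". Medications that lower these electrolytes are given as a further example.

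The Serum Electrolytes row of Table 7.2.4 names the same four analytes at grade 3 or higher, "Calcium, Potassium, Magnesium, Phosphorous", and attributes the abnormality to irinotecan by way of diarrhea. Its action is: "Provide supportive care per Section 6.7. Maintain treatment per investigator discretion".

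Table 10 has one scheduled chemistry row, the "Comprehensive Metabolic Panel bb". Footnote bb gives its contents: "Comprehensive metabolic panel: Sodium, potassium, chloride, carbon dioxide, creatinine, urea nitrogen, calcium, glucose, albumin, total bilirubin, alkaline phosphatase, total protein", then the two transaminases.

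The DLT definition (Section 5.3.3) has no electrolyte criterion. A related electrolyte event in cycle 1 would fall under the generic non-hematological criteria. Criterion 8 is "Grade 3 toxicity despite maximal medical therapy lasting > 7 days". Criterion 9 is a grade 3 event leading to permanent discontinuation. Criterion 10 is any grade 4 event other than diarrhea that responds to treatment within 3 days.

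**The concern.** The protocol foresees these abnormalities as a consequence of irinotecan and says what to do when one reaches grade 3. For two of the four electrolytes, however, the calendar never produces the value that would show it.

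Three things depend on that value.

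- **Detection.** Without a scheduled test, an abnormality with no symptoms is found only if someone has another reason to order the assay.
- **Baseline.** Section 7.2.1 takes baseline values from screening. Sections 7.2.1 and 7.2.2 let a pre-existing laboratory abnormality be judged against its starting grade. For magnesium and phosphorus no starting grade is planned.
- **The primary endpoint.** The trial escalates by a 3+3 rule on DLTs, and the RP2D rests on the full toxicity profile. If a class of laboratory toxicity is looked for in some patients and not in others, the counts are not ascertained on the same footing across patients or dose levels.

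**Working it through.** The plan gives no figure to reproduce on this point. The check compares lists and then follows the consequences.

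**Step 1: named analytes against scheduled analytes.** Footnote bb lists 14: sodium, potassium, chloride, carbon dioxide, creatinine, urea nitrogen, calcium, glucose, albumin, total bilirubin, alkaline phosphatase, total protein and two transaminases.

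| Electrolyte | Section 6.1.8 | Table 7.2.4 | Footnote bb |
|---|---|---|---|
| Potassium | named | named | listed |
| Calcium | named | named | listed |
| Magnesium | named | named | not listed |
| Phosphorus | named | named | not listed |

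Two of four are covered and two are not. Alkaline phosphatase is an enzyme and does not stand in for serum phosphorus.

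**Step 2: is either analyte scheduled elsewhere?** No other row or footnote of Table 10 includes magnesium or phosphorus, and no other section schedules them. The introduction to Section 10 allows procedures to be done more often when clinically indicated. That changes how often the listed panel is drawn, not what it contains.

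**Step 3: what produces a result?** Only the extra-testing clause in Section 6.1.8. Its examples include prior low values, gastrointestinal toxicity and relevant medications. The first needs an earlier measurement, which the calendar does not supply. The other two need none, but they apply only to patients in those circumstances and rest on clinical judgment. Footnote c also lets laboratory work be done at a local clinic, where tests outside the listed panel may vary.

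**Step 4: which DLT criteria are exposed?** Each requires onset in the first cycle (including the Cycle 2 Day 1 safety assessments) and at least possible attribution.

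- Criterion 8 requires grade 3 to persist beyond 7 days despite maximal therapy. A value that was never seen was never treated, so an undetected event does not plainly meet it.
- Criterion 9 requires permanent discontinuation, which an unseen value would not cause.
- Criterion 10 takes any related grade 4 event, with an exception only for responsive diarrhea. A related grade 4 magnesium or phosphorus value in cycle 1 would count. This is the criterion for which unscheduled detection matters.

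**Step 5: what one unseen event changes under the 3+3 rule in Section 5.3.**

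| True DLT count | Count if one is unseen | Action on true count | Action on observed count |
|---|---|---|---|
| 1 of 3 | 0 of 3 | enroll 3 more at the same level | escalate |
| 2 of 3 | 1 of 3 | MTD exceeded | enroll 3 more at the same level |
| 2 of 6 | 1 of 6 | MTD exceeded | escalate |

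In each row a single missed event changes the cohort decision, and always towards the less cautious action. How often this would happen cannot be computed, because the documents give no rate of grade 3 or 4 magnesium or phosphorus abnormality.

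**The case against.** The strongest reply is that the protocol does provide for testing, through the route it expects to matter. Table 7.2.4 gives diarrhea as the mechanism, and Section 6.1.8 names gastrointestinal toxicity as a reason to test. A patient with marked diarrhea would probably be tested, and any result, scheduled or not, brings the correction rule and the DLT criteria into play. This stands, and it rules out several stronger readings.

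- A reader might infer that the electrolyte rule cannot operate for magnesium and phosphorus. It can, once a value exists.
- A reader might infer that electrolyte-specific DLT criteria have been disabled. There are none; criteria 8 to 10 are generic and apply normally to any value obtained.
- A reader might infer that Table 7.2.4 demands immediate correction. Only Section 6.1.8 uses that urgency. The table asks for supportive care, leaves continued treatment to the investigator and imposes no hold or dose reduction, so no mandatory dosing rule is defeated.
- A reader might infer that the analytes are missed at every visit. The panel itself is drawn at only some visits, so the comparison is with those draws.

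It is also fair to say that no harm has been quantified. What the reply does not remove is the dependence on judgment: patients without symptoms or an obvious trigger have no planned value, and no patient has a planned baseline.

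**Conclusion.** The mismatch is real and can be verified from the text. Two of the four electrolytes named for action at grade 3 or higher have no scheduled measurement, at screening or on treatment, for any patient (6 to 53 possible, 29 anticipated). Abnormalities in these two are not systematically ascertained and may be found unevenly between patients. The part that touches the primary endpoint is narrow: a related, asymptomatic grade 4 value in cycle 1.

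The conclusion assumes that footnote bb is the complete content of the panel and that sites run what the protocol lists. If the local panel routinely includes both analytes, the practical gap is smaller, but the protocol does not say so. The documents do not support a claim that the MTD or RP2D would be wrong. They support the claim that one toxicity the protocol anticipates is not looked for in a uniform way. It should be corrected, because the trial's main output is a toxicity count in small cohorts and the correction is minor.

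**What to change.** Reconcile footnote bb with Section 6.1.8 and Table 7.2.4 by adding magnesium and phosphorus to the listed panel, measured at the time points where the panel is already drawn, including screening. This changes measurement only and leaves every dosing and treatment rule as it is.

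The cost is two assays per draw and one footnote edit, with no new visit. The documents do not state tube volumes, so whether the existing sample suffices should be confirmed with the laboratory. Where a local clinic is used, the order must name both tests. Abnormalities arising between draws would still depend on indicated testing.

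The alternative is to state that the two are tested only when indicated. That removes the contradiction but leaves detection uneven and the baseline missing.

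The same amendment can clear two slips in these passages. Table 7.2.4 sends the reader to Section 6.7, but the contents list ends Section 6 at 6.2 and the text meant appears to be Section 6.1.8. The heading of Section 6.1.8 cites CTCAE version 3 while its body cites version 4.
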